6.12.4. Deaths, Other Serious Adverse Events, and Other Notable Adverse Events

The following are "notable" events, from start of study drug through end of study participation:

- Deaths
- SAEs, and
- Discontinuations of study treatment due to AEs.

Narratives (patient-level data and summary paragraph) will be provided for participants in the safety population with at least 1 notable event.

Safety topics of interest are not considered notable events, unless 1 of the above criteria is met. Displays with individual patient-level data will be created for safety topics of interest using various formats such as a customized listing and/or a customized graphical patient profile as specified in the section associated with the safety topic of interest. Medical case summaries/vignettes will be provided if deemed relevant for the discussion of the safety topic of interest.

6.12.5. Hospitalization, Clinical Events, Clinical Status, and Environmental Risk Factors

The following events (observed at any time point during the treatment and assessment period) will be analyzed with the method described in Section 6.16.2.7 and Section 6.16.2.9:

- Proportion of participants hospitalized
- Duration of hospitalization (DOH; in days),
- proportion (percentage) of participants admitted to intensive care unit (ICU),
- proportion (percentage) of participants requiring mechanical ventilation (oxygen source = "Intubation/Mechanical Ventilation")

All hospitalization events, procedures of special interest, and environmental risk factors will be listed.

In the event that a participant has an ongoing hospitalization event at the time of study disposition, the hospitalization end date will be imputed to the study disposition date.

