6.1.3. Study Time Intervals

To calculate the length of any time interval or time period in this study, the following formula will be used:

 $Length\ of\ interval\ (days) = End\ Date - Interval\ Start\ Date + 1$

To convert any time length from days to weeks, the following formula will be used:

Length of interval (weeks) = Length of interval (days)/7

Only for the purpose of calculating the length of study period time intervals, the words "prior to" in Table PYAH.6.2 should be understood to mean "the day before" while the words "after" should be understood to mean "the day after." For the purpose of determining whether a date/time lies within an interval, these words are intended to convey whether the start or end of the period is inclusive of the specified date.

Study Period	Interval Start Definition	Interval End Definition
Screening: All participants who sign informed consent are considered as entering the Screening Period.	Informed consent date	Prior to the start of Treatment and Assessment Period.
Treatment and Assessment Period: All participants who are randomized to the study are considered as entering the treatment and assessment period.	At the start of study drug administration date/time following randomization. For participants who are randomized but not dosed, the treatment and assessment period starts on the date of randomization.	The minimum of treatment and assessment period discontinued date, study discontinuation date, or first post treatment follow-up visit date.
Post-Treatment Follow-Up: All participants who had a follow up visit are considered as entering follow-up period.	After the Treatment and Assessment Period ends.	The maximum of the last study visit date or study disposition date.

Table PYAH.6.2. Definition of Study Period Time Intervals

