6.16.2.7. Duration of Hospitalization

Treatment comparisons of the mean DOH (in days) will be compared between active treatment and placebo will be made using nonparametric rank-sum test (such as Mann-Whitney or van Elteren test).

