The secondary efficacy endpoints will be summarized by treatment group and infusion rate and administration, as appropriate, in a similar manner as the main study (see Section 6.10).

The exploratory efficacy objectives for the substudies are to characterize overall participant clinical status, viral load, and symptom resolution and improvement. The following are the exploratory efficacy endpoints:

- For addendum (2) CCI
 - Proportion (percentage) of participants who experience these events by Day 22,
 29, 60, and 85
 - COVID-19 related hospitalization (defined as ≥24 hours of acute care)
 - Death from any cause
 - o Proportion (percentage) of participants who experience these events by Day 29
 - COVID-19 related hospitalization (defined as ≥24 hours of acute care),
 - COVID-19 related emergency room visit, or

- Death from any cause
- Time to symptom resolution
- o Proportion of participants demonstrating symptom resolution via the symptom questionnaire on Days 3, 5, 7, 11, 22, and 29
- o Change in symptom score (total of ratings) from baseline up to Days 7, 11, 22, and 29.
- Time to symptom improvement
- o Proportion of participants demonstrating symptom improvement via the symptom questionnaire on Days 3, 5, 7, 11, 22, and 29
- For addendum (4):
 - Duration, in days, of hospitalizations,
 - o Proportion of participants admitted to the ICU
 - o Proportion of participants requiring mechanical ventilation
 - o Proportion of participants that achieve SARS-CoV-2 clearance (Days 3, 5, 7, 11, and 29)
 - o 75th percentile of SARS-CoV-2 viral load at Day 7
 - Characterize emergence of viral resistance to LY3853113

The exploratory efficacy endpoints will be summarized by treatment group and infusion rate and/or administration route in a similar manner as the main study (see Section 6.10).

Additional analyses may be performed for the substudies.

An interim analysis of safety data may be conducted at any time for participants who have reached Day 3.

7. References

Firth D. Bias reduction of maximum likelihood estimates. *Biometrika*. 1993;80(1):27-38. https://doi.org/10.2307/2336755

8. Appendices

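### Duration of hospitalization (Arms 1-11): stays cut off by death or inpatient withdrawal are ranked as completed stays, and the SAP does not say which participants are ranked

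*SAP*

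**What the plan says.** Section 6.12.5 lists duration of hospitalization among events "observed at any time point during the treatment and assessment period". It says that these events "will be analyzed with the method described in Section 6.16.2.7 and Section 6.16.2.9". When a participant "has an ongoing hospitalization event at the time of study disposition, the hospitalization end date will be imputed to the study disposition date". No exception is made for death or withdrawal.

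Section 6.16.2.7 gives the method in one sentence: "Treatment comparisons of the mean DOH (in days) will be compared between active treatment and placebo will be made using nonparametric rank-sum test". It names Mann-Whitney and van Elteren as examples. It does not say whether never-admitted participants are left out or entered at 0 days.

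Section 6.1.3 fixes how length is computed ("To calculate the length of any time interval or time period in this study, the following formula will be used"): end date minus start date plus 1. An earlier end date therefore gives a shorter stay.

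Elsewhere the SAP does give death a place. Section 6.3.6 sets symptom values missing after death to the worst category, Appendix 3 scores death as the lowest NIAID value, and Sections 6.10.3.3.1 and 6.10.3.3.2 count death as an event. Duration of hospitalization has no such rule.

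**The concern.** A rank-sum test takes each value as a completed observation, and for length of stay a lower value reads as better. Death in hospital and withdrawal while an inpatient both end the recorded stay early without the recovery that a short stay is taken to mean. With nothing in the plan to mark such values as truncated or to rank death as worst, a treatment that prevents early in-hospital deaths could appear to lengthen hospital stay, and one with more such deaths could appear to shorten it. Where few participants are admitted, a handful of these stays can settle the direction of the result.

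The effect depends on who is ranked, which the plan leaves open.

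**Working it through.** The SAP gives no figure for this comparison, so there is nothing of its own to reproduce. The rules come from Sections 6.1.3, 6.12.5 and 6.16.2.7, and the 122 per arm from Section 5.2 (Arms 9-11). All stay lengths and death rates below are assumed.

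**Length of stay.** Admitted Day 5, died in hospital Day 7, disposition date taken as the date of death: 7 - 5 + 1 = 3 days. Admitted Day 5, discharged alive Day 14: 14 - 5 + 1 = 10 days. On length alone the death ranks better.

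**Hospitalized participants only, 6 per arm.** Placebo: deaths after 3, 3 and 4 days, live discharges at 8, 9 and 10. Active, with those deaths averted: 8, 9, 9, 10, 10 and 11. For each active stay, U counts the placebo stays that are shorter, plus one half for each tie.

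- As written: U = 3.5 + 4.5 + 4.5 + 5.5 + 5.5 + 6 = 29.5 of 36, or 0.82 (asymptotic two-sided p = 0.073). The medians are 9.5 days on active and 6 on placebo, so active looks worse.
- Deaths ranked worst: U = 0.5 + 1.5 + 1.5 + 2.5 + 2.5 + 3 = 11.5 of 36, or 0.32 (p = 0.325). The direction now favours active.

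**The same data, 122 per arm, 116 never admitted at 0 days.** U = 116 × 116 / 2 + 6 × 116 + U among the admitted = 6728 + 696 + U. The null value is 122 × 122 / 2 = 7442.

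- As written: 6728 + 696 + 29.5 = 7453.5, and 7453.5 / 14884 = 0.501 (p = 0.96).
- Deaths ranked worst: 6728 + 696 + 11.5 = 7435.5, and 7435.5 / 14884 = 0.4996 (p = 0.98).

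The sign still changes, but the size is negligible.

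**Range of rates, by simulation (2,000 replicates per setting).** Assumed: stay to live discharge lognormal with median 8 days and log-SD 0.6; 8 or 20 admissions per arm; a share of active inpatients dying or withdrawing on stay day 2 to 7, none on placebo; no other difference. Entries are the probability that an active stay is the longer; 0.50 means no difference and a lower value favours active.

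| Share dying or withdrawing on active | Cut-off as written, hospitalized only | Those participants ranked worst, hospitalized only |
|---|---|---|
| 10% | 0.46-0.47 | 0.55-0.56 |
| 20% | 0.43-0.44 | 0.60-0.61 |
| 40% | 0.35 | 0.70 |

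With all 122 per arm ranked and the rest at 0 days, the values across these settings are 0.496-0.500 as written and 0.500-0.505 with worst rank.

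**The case against.** Several points on the other side stand.

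- **The ranked population.** The reversal is material only if hospitalized participants alone are ranked. Reference to a mean duration suggests that set, but Section 6.16.2.7 does not say so. A reader might infer that the comparison is misleading on any reading; the 0-day calculation shows that it is not.
- **The example is extreme.** Three early deaths among six placebo inpatients, all averted, has no support in the SAP, whose population has mild to moderate illness. Even so, neither p-value falls below 0.05. At a 10% rate the shift is a few hundredths either side of 0.50.
- **The end-date rule is not the whole cause.** The SAP does not define the disposition date for a death. A site may record death as the end of the stay, and the stay is then just as short without imputation. What remains in either case is that no rank is given to death. Nor is every imputed stay short: one still open at the end of planned follow-up, or ended by a late death, can be long.
- **Reach.** Arms 12-14 are descriptive only (Section 6.1.4), and the addendum populations have no inferential comparisons (Section 6.19.1). Addendum (4) lists "Duration, in days, of hospitalizations" as an exploratory endpoint, so one might infer that the same distorted test is run there. It is not.
- **Death is visible elsewhere.** It enters both composite clinical-status endpoints, the NIAID score and the narratives, and all hospitalization events are listed. That limits the harm, although it does not correct the ranking itself.

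**Conclusion.** For Arms 1-11 the gap is real and minor. Followed as written, the plan ranks a stay cut off by death or inpatient withdrawal as a completed stay. If only hospitalized participants are ranked, such a stay tends to rank better than a longer one ending in live discharge, and the comparison can point the wrong way: 0.82 against 0.32 in the assumed example, and 0.35 against 0.70 at an assumed 40% early loss. If never-admitted participants are ranked at 0 days, the effect is negligible. The SAP does not say which applies.

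These sizes rest on assumed stays and rates, and on the disposition date (or the recorded end of stay) being the date of death or withdrawal. A reader might go further and infer that a main efficacy or safety conclusion is at risk. The document does not support that. The method sits among the exploratory analyses not defined in the protocol (Section 6.16.2), duration of hospitalization is in none of the objective tables of Section 4, and the secondary clinical-status endpoints count death.

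**What to change.** In Section 6.16.2.7:

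- State which participants are ranked, preferably the whole safety population with never admitted = 0 days.
- Give death by Day 29 the worst rank.
- Treat inpatient withdrawals as truncated, with a sensitivity analysis that bounds their stay: once ending at the withdrawal date, once counted as hospitalized through Day 29.
- Show deaths by arm beside the result, and describe raw length of stay only among those discharged alive.

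Days alive and out of hospital through Day 29 would be an acceptable alternative, but the gap does not require a new measure. Nor does it require every inpatient withdrawal to be counted as hospitalized through Day 29 in the main analysis.

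The cost is SAP wording and one re-derived variable from dates already collected. The downside is small: the ranked measure combines death with stay, and with everyone ranked most values are tied at 0 (116 of 122 per arm in the example), so it says little about length of stay among those admitted. The descriptive summary covers that for participants discharged alive.

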6.12.6. Clinical Laboratory Evaluation

Laboratory analyses will include planned analytes only. Planned analytes are those specified in the protocol (See Protocol Appendix 2). However, unscheduled measurements of planned analytes will be included/excluded as specified in the relevant sections. Examples of unplanned

measurements include those that the clinical investigator orders as a repeat test or "retest" of a laboratory test in case of an abnormal value, and those the investigator orders for a "follow-up visit" due to clinical concerns. Some planned analytes are intended for individual case reviews and will not be included in group-level summaries.

Investigative sites may use a local laboratory instead of a central laboratory for reporting the hematology and clinical chemistry analytes. Individual laboratory results reported using a local laboratory will be transformed such that a standardized result is used in the analysis. The transformation will be made using the calculation below:

$$s = L_s + (x - L_x) \frac{U_s - L_s}{U_r - L_r}$$

Where,

- S = the transformed individual laboratory value to a common standard laboratory reference range
- x = the individual local laboratory value
- L_x and U_x = lower and upper limits of normal range for the corresponding laboratory analyte, and
- L_s and U_s = lower and upper limits of normal range for the corresponding laboratory analyte from the central laboratory.

6.12.7. Vital Signs and Other Physical Findings

The planned summaries are provided in Table PYAH.6.9. The measurements analyzed for vital signs and physical characteristics include systolic blood pressure (BP), diastolic BP, pulse, weight, peripheral oxygen saturation (SpO₂), respiratory rate, fraction of inspired oxygen (FiO₂), and temperature if data warrant.

The criteria for identifying subjects with treatment-emergent abnormalities are based on Table PYAH.6.10.

Some of the analyses of vital signs may be incorporated into interactive display tools instead of or in addition to a static display. Any display described in Table PYAH.6.9 and not provided would be available upon request. For example, box plots for observed values, scatter plots, and shift tables could be provided as interactive displays for medical review.

Table PYAH.6.9. Tables and Figures Produced to Support Vital Signs and Physical Characteristics

Analysis Type	Analysis Details		
Box plots for observed	Includes participants who have both a baseline and a postbaseline measurement from		
values by visit	a planned visit.		
	Unplanned measurements will be excluded.		
	Last baseline will be used.		
	Descriptive summary statistics will be included in a table below the box plot.		
	No inferential statistics.		
Box plots for change	Includes participants who have both a baseline and a postbaseline planned		
from baseline values by	measurement.		
visit	Unplanned measurements will be excluded.		
	Last baseline will be used.		
	Descriptive summary statistics will be included in a table below the box plot.		
	Change from last baseline to last postbaseline will also be summarized within the		
	box plot of changes (rightmost column), and descriptive summary statistics will be		
	included in a table below the box plot along with a p-value using the ANCOVA		
	model.		
Scatter plots of	Includes participants who have both a baseline and postbaseline observation.		
baseline-by-maximum	Unplanned measurements will be included.		
values and baseline-by-	Lines indicating the reference limits will be included.		
minimum values	Max vs Max: Maximum baseline versus maximum postbaseline.		
	Min vs Min: Minimum baseline versus minimum postbaseline.		
Summary tables for	Limits provided by the central lab service will be used to define low and high.		
shifts to high/low	Normal/high to low: Includes the number and percentage of participants by		
	treatment whose minimum baseline result is normal or high and whose minimum		
	postbaseline result is low.		
	 Denominator equals participants whose minimum baseline result is normal 		
	or high and who have at least 1 postbaseline result.		
	Normal/low to high: Includes the number and percentage of participants by		
	treatment whose maximum baseline result is normal or low and whose maximum		
	postbaseline result is high.		
	o Denominator equals participants whose maximum baseline result is normal		
	or low and who have at least 1 result during the treatment and assessment		
	period.		
	Statistical comparisons will be included.		

Abbreviations: ANCOVA = analysis of covariance; Max = maximum; Min = minimum.

Table PYAH.6.10. Categorical Criteria for Abnormal Treatment-Emergent Blood Pressure and Pulse Measurement, and Categorical Criteria for Weight and Temperature Changes

Parameter	Age Group	Low	High
Systolic BP (mm Hg)	12 years	≤85 and decrease from	≥126 and increase from
(Supine or sitting –		baseline ≥20	baseline ≥20
forearm at heart level)	13-17 years	≤90 and decrease from	≥129 and increase from
		baseline ≥20	baseline ≥20
	≥18 years	≤90 and decrease from	≥140 and increase from
		baseline ≥20	baseline ≥20
Diastolic BP (mm Hg)	12 years	≤50 and decrease from	≥82 and increase from
(Supine or sitting –		baseline ≥10	baseline ≥10
forearm at heart level)	13-17 years	≤50 and decrease from	≥86 and increase from
		baseline ≥10	baseline ≥10
	≥18 years	≤50 and decrease from	≥90 and increase from
		baseline ≥10	baseline ≥10
Pulse (bpm)	12 years	<60 and decrease from	>140 and increase from
(Supine or sitting)		baseline ≥25	baseline ≥25
	13-17 years	<50 and decrease from	>120 and increase from
		baseline ≥15	baseline ≥15
	≥18 years	< 50 and decrease from	>100 and increase from
		baseline ≥15	baseline ≥15
Temperature	All	<96°F (<35.6°C) and	≥101°F (≥38.3°C) and
		decrease ≥2°F (≥1.1°C)	increase ≥2°F (≥1.1°C)
		from baseline	from baseline

Abbreviations: BP = blood pressure; bpm = beats per minute.

6.12.8. Electrocardiograms

Results of electrocardiograms (ECGs) performed during the study will not be reported.

6.12.9. Immunogenicity

If data from validated immunogenicity assays are available, treatment-emergent antidrug antibodies (TE-ADAs) may be assessed.

Treatment-emergent ADAs are defined as participants

- with a 2-fold (1 dilution) increase in titer compared with the minimum required dilution if no antidrug antibodies (ADAs) were detected at baseline (treatment-induced ADA) or
- with a 4-fold (2 dilutions) increase in titer compared with baseline if ADAs were detected at baseline (treatment-boosted ADA).

The frequency and percentage of participants with preexisting ADAs and who are TE-ADA positive (TE-ADA+) to LY3853113, LY3819253, LY3832479, and/or VIR-7831 may be tabulated.

The distribution of titers and frequency of neutralizing antibodies (if assessed) for the TE-ADA+ participants may also be tabulated.

The relationship between the presence of antibodies and PK parameters, efficacy response, or safety to LY3853113, LY3819253, LY3832479, and/or VIR-7831 may also be assessed.

6.13. Subgroup Analyses

This study is not powered for subgroup analyses; therefore, all subgroup analyses will be treated as exploratory.

Subgroup analyses will be conducted for the primary endpoint. Subgroups may include:

- time from symptom onset to study randomization
- baseline severity of COVID-19
- age group (<35, \ge 35 to <45, \ge 45 to <55, >55 years old)
- gender (male, female)
- race
- ethnicity
- baseline weight ($<60 \text{ kg}, \ge 60 \text{ to } <100 \text{ kg}, \ge 100 \text{ kg}$)
- baseline body mass index (underweight to normal: <25 kg/m², overweight: ≥25 to <30 kg/m² and obese: ≥30 kg/m²)
- concomitant medication of interest use (yes/no)

Treatment group differences will be evaluated within each category of the subgroup regardless of whether the interaction is statistically significant. If any group within the subgroup is <10% of the total population, only summaries of the efficacy data will be provided; i.e., no inferential testing.

The analysis of additional subgroups and/or subgroup analyses on additional endpoints will not require an amendment to the SAP.

Within each subgroup category the relevant summary measure by treatment, treatment differences (compared to placebo) and 95% CIs will be displayed. Also, p-values using appropriate statistical tests for treatment comparison will be provided. Forest plots may be generated to display the treatment difference and 95% CIs for selected efficacy subgroup analyses.

Baseline severity of COVID-19 will be defined using the following definition.

- Severity will be defined to be Moderate if the participant demonstrates the following at baseline:
 - Symptoms:
 - Shortness of breath (with symptom questionnaire severity score ≥1)

OR

 Symptoms of moderate illness with COVID-19, (any symptom questionnaire score >1, excluding loss of appetite)

AND

- Clinical signs suggestive of moderate illness with COVID-19, such as:
 - Respiration rate ≥20 breaths per minute

OR

- Pulse ≥90 beats per minute.
- Else, severity will be defined to be Mild.

Concomitant therapies of interest include remdesivir, lopinavir/ritonavir, chloroquine, hydroxychloroquine, anticoagulants, dexamethasone, or other investigational interventions. Details of the medications included in this subgroup are provided below in Table PYAH.6.11.

Table PYAH.6.11. Concomitant Medications of Interest Subgroup

Drug name	ATC Code	Who Drug Preferred Term
Remdesivir		REMDESIVIR
Kaletra	J05AR	KALETRA
Lopinavir	J05AR	LOPINAVIR
Hydroxychloroquine	P01BA	HYDROXYCHLOROQUINE
Chloroquine	P01BA	CHLOROQUINE
Baricitinib	L04AA	BARICITINIB
Heparin	B01AB	HEPARIN
Fondaparinux	B01AX	FONDAPARINUX
Argatroban	B01AE	ARGATROBAN
Dexamethasone	H02AB	DEXAMETHASONE

Abbreviation: ATC = anatomical therapeutic chemical.

Treatment Arms 12-14

Subgroup analyses (\geq 12 and <18 years old versus \geq 18 years old) may be performed on all analyses and include descriptive statistics only. Subgroup analyses for SARS-CoV-2 vaccine status may be performed.

Subgroups for baseline age and baseline BMI will be defined as:

- baseline age groups
 - \circ \geq 12 to <18, \geq 18 to <35, \geq 35 to <45, \geq 45 to <55, \geq 55 to <65, \geq 65 years old
 - \circ <65, \geq 65 years old
 - \circ <65, \geq 65 to <75, \geq 75 to <85, \geq 85 years old; and
 - \circ \geq 12 to \leq 18, \geq 18 years old

- baseline BMI groups (based on Centers for Disease Control and Prevention (CDC) growth charts)
 - o Group 1:
 - age <18 years old and
 - ➤ BMI <85th percentile for their age and gender based on Centers for Disease Control and Prevention (CDC) growth charts
 - ➤ BMI ≥85th percentile for their age and gender based on CDC growth charts
 - age ≥18 years old and
 - ➤ For Treatment Arms 12-13, BMI <35 kg/m², or for Treatment Arm 14, BMI <25 kg/m²
 - ➤ For Treatment Arms 12-13, BMI ≥35 kg/m², or for Treatment Arm 14, BMI ≥25 kg/m²
 - o Group 2:
 - age <18 years old and
 - ➤ Underweight (BMI <5th percentile)
 - ➤ Normal (BMI 5th percentile to < 85th percentile)
 - ➤ Overweight (BMI 85th percentile to <95th percentile)
 - ➤ Obese (BMI ≥95th percentile)
 - age ≥18 years old and
 - ➤ Underweight or normal (BMI <25 kg/m²)
 - ➤ Overweight (BMI ≥25 to <30 kg/m²)
 - ightharpoonup Obese (BMI \geq 30 to \leq 40 kg/m²), and
 - ➤ Extreme obese (BMI ≥40 kg/m²)

Subgroup analyses for high-risk status will not be performed. Other subgroup analyses may be conducted if there is sufficient sample size within the subgroups.

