 Characteristics Age groups (<35, ≥35 to <45, ≥45 to <55, >55 years old) Sex Race (American Indian or Alaska Native, Asian, Black or African American, Native Hawaiian or Other Pacific Islander, White, Multiple) Ethnicity (Hispanic or Latino, Not Hispanic or Latino, Not Reported) Height Weight Body mass index (BMI), and Days since COVID-19 symptom onset. Days since COVID-19 symptom onset (≤8 days, >8 days) SpO₂ SpO₂ category (<96%, ≥96%) COVID-19 disease severity category Statistics to be included: Continuous: Mean, standard deviation, min, max, median, and first quartile and third quartile Categorical: n and percent (denominator for percentages will be the number of participants with nonmissing values) A column that combines all treatment groups (i.e., a total column) will be included (applicable to controlled analysis sets) No inferential statistics For Treatment Arms 12-14: • The age groups are defined as: 				
 Characteristics Age groups (<35, ≥35 to <45, ≥45 to <55, >55 years old) Sex Race (American Indian or Alaska Native, Asian, Black or African American, Native Hawaiian or Other Pacific Islander, White, Multiple) Ethnicity (Hispanic or Latino, Not Hispanic or Latino, Not Reported) Height Weight Body mass index (BMI), and Days since COVID-19 symptom onset. Days since COVID-19 symptom onset (≤8 days, >8 days) SpO₂ SpO₂ category (<96%, ≥96%) COVID-19 disease severity category Statistics to be included: Continuous: Mean, standard deviation, min, max, median, and first quartile and third quartile Categorical: n and percent (denominator for percentages will be the number of participants with nonmissing values) A column that combines all treatment groups (i.e., a total column) will be included (applicable to controlled analysis sets) No inferential statistics For Treatment Arms 12-14: • The age groups are defined as: 	Demographic			

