n and percent (denominator for percentages will be the number of participants with nonmissing values) A column that combines all treatment groups (i.e., a total column) will be included (applicable to controlled analysis sets) No inferential statistics For Treatment Arms 12-14: • The age groups are defined as:		Mean, standard deviation, min, max, median, and first quartile and third quartile		
nonmissing values) A column that combines all treatment groups (i.e., a total column) will be included (applicable to controlled analysis sets) No inferential statistics For Treatment Arms 12-14: • The age groups are defined as:				
A column that combines all treatment groups (i.e., a total column) will be included (applicable to controlled analysis sets) No inferential statistics For Treatment Arms 12-14: • The age groups are defined as:				
(applicable to controlled analysis sets) No inferential statistics For Treatment Arms 12-14: • The age groups are defined as:		,		
No inferential statistics For Treatment Arms 12-14: • The age groups are defined as:		(applicable to controlled analysis sets)		
For Treatment Arms 12-14: • The age groups are defined as:				
The age groups are defined as:		No inferential statistics		
The age groups are defined as:		For Treatment Arms 12-14:		
		o Age groups (<65, ≥65 years old), (≥12 to <18, ≥18 to <35, ≥35 to <45, ≥45 to <55, ≥55 to <65, ≥65 years old), (<65, ≥65 to <75, ≥75 to <85, ≥85 years		
• The following additional groups are defined:				
Baseline SARS-CoV-2 vaccine status				
SARS-CoV-2 vaccination during the study				
Medical History Number and percentage of participants with medical history events and preexisting	Medical History			
and Preexisting conditions using MedDRA PT nested within SOC	_			
conditions • Ordered by decreasing frequency within SOC on the LY total arm				
Preexisting conditions are defined as those conditions with a start date prior to the first doe		Preexisting conditions are defined as those conditions with a start date prior to the first dose		
		of the study drug and stop dates that are at or after the informed consent date or have no stop		
date (i.e., are ongoing).				
	Prior Therapy of	Number and percentage of participants with prior medication of interest will be displayed as		
Interest "Prior medications"	nterest	"Prior medications"		
Listing	Listing			
Demographics				

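### The default age categories in SAP Section 6.13 and Table PYAH.6.5 leave age 55 in no group

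*SAP*

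**What the plan says.** SAP Section 6.13 provides that "Subgroup analyses will be conducted for the primary endpoint" and names age group among the subgroups that may be used. The last two age categories in that list meet at "<55, >55 years old". Table PYAH.6.5 in Section 6.7 sets the same categories for the baseline summary: "Age groups (<35, ≥35 to <45, ≥45 to <55, >55 years old".

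Treatment Arms 12-14 have their own age groups. In Table PYAH.6.5 their finest split runs "≥45 to <55, ≥55 to <65, ≥65 years old", and the Arms 12-14 part of Section 6.13 uses the same cut at 55. The four-category list is thus the operative one for Arms 1-11.

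Section 6.13 also says what is produced within each subgroup category: summaries by treatment, differences from placebo with 95% confidence intervals, and p-values. Inferential testing is withheld if any category holds less than 10% of the total population.

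**The concern.** A participant aged 55 is neither below 55 nor above it, so the four categories do not cover the population. If the list is programmed literally, three things follow.

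- The age-subgroup estimates, intervals and tests for the primary endpoint omit participants aged 55, and the age rows do not sum to the analysis population.
- Table PYAH.6.5 bases percentages on participants with nonmissing values. A 55-year-old has a known age but no age category. Either the percentages fall short of 100%, or the category is treated as missing and the denominator shrinks. The SAP does not say which.
- The oldest category is smaller than intended. If it lies close to the 10% limit, the loss could decide whether any age-subgroup test is run.

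If a programmer quietly corrects the sign instead, the output departs from the approved SAP.

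**Working it through.** The plan states no figure to reproduce. The check is whether the printed intervals cover every age exactly once.

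**1. Coverage.** Each whole-year age was assigned to the printed categories, from 18 to 100 for the default list and from 12 to 100 for the six-category Arms 12-14 list.

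| List | Ages in no category | Ages in more than one |
|---|---|---|
| Default: <35; 35 to <45; 45 to <55; >55 | 55 | none |
| Default with the last category read as ≥55 | none | none |
| Arms 12-14, six categories | none | none |

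**2. Is the gap intended?** The other numeric groupings in the same Section 6.13 list, for weight and body mass index, close every boundary with ≥ at the lower limit. So do the default age categories at 35 and 45, and the Arms 12-14 list at 55. Nothing in the SAP says that age 55 is to be left out.

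**3. How many participants?** Planned sizes come from Section 5.2:

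- Arms 1-6: four arms of 100 and two of 150, so 4 × 100 + 2 × 150 = 700
- Arms 7-8: 2 × 100 = 200
- Arms 9-11: 3 × 122 = 366

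The SAP gives no age distribution, so the share *s* aged 55 is an assumption, varied from 1% to 3%. Expected number affected = N × *s*.

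| Arms | N | *s* = 1% | *s* = 2% | *s* = 3% |
|---|---|---|---|---|
| 1-6 | 700 | 7.0 | 14.0 | 21.0 |
| 7-8 | 200 | 2.0 | 4.0 | 6.0 |
| 9-11 | 366 | 3.7 | 7.3 | 11.0 |

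**The case against.** The best case on the other side is that this is an evident typing slip with little effect. Participants aged 55 remain in the primary analysis, the continuous age summary and every other subgroup. No primary or secondary result, power figure or error rate changes. Section 6.13 is explicit: "This study is not powered for subgroup analyses; therefore, all subgroup analyses will be treated as exploratory". Age is listed only as a subgroup that may be used. A programmer would probably notice that the age rows do not add up and ask. All of this stands, and it limits the weight of the point. It does not fill the gap, and the baseline table is not optional in the way the subgroup is.

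A second objection is that the sign may have been lost when the PDF was read. Inequality signs are uneven elsewhere in the text: the adolescent cut at 18 appears with different signs within Section 6.13. A reading error cannot be excluded entirely, but it is unlikely. The strict sign at 55 occurs in two separate sections, and each keeps ≥ at 35 and 45 on the same line.

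Third, the number affected is uncertain. The share aged 55 is assumed. Arms 9-11 enrol low-risk participants, and any age limit would be in the protocol, which is not at hand, so their number could be lower. If age were stored as a decimal, only a value of exactly 55.0 would be lost. These points stand, and the counts should be read as a range under stated assumptions.

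**Conclusion.** The concern holds. As written, age 55 is the only whole-year age without a category in the default list, and the omission occurs in both places where that list is set out. It affects Arms 1-11 only. The loss is confined to the age-category rows of the baseline table and the age-subgroup results for the primary endpoint. With age in completed years and 1% to 3% of participants aged 55, it amounts to about 7-21 participants in Arms 1-6, 2-6 in Arms 7-8 and 4-11 in Arms 9-11. This is a minor correction with no bearing on the primary inference.

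**What to change.** In Section 6.13 and in the default age-group row of Table PYAH.6.5, change the last category from >55 to ≥55. Every age from 18 to 100 then falls in exactly one category, in line with the cut at 55 already used for Arms 12-14.

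The edit is one character in two places. The SAP revision history for Version 7 refers to post hoc analyses of Arms 1-6 already carried out, so some age-group output may exist. Check how age 55 was handled in any such output, and rerun the age tables if it was left out.
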